15. Tumor assessment: All patients will undergo MRI, chest, abdomen, pelvis and bone examination at baseline period, and subsequent imageological examination included the chest, abdomen, pelvis, and other metastatic sites, if any. The preferred imaging methodology is CT enhanced scan, and using the same imaging examination method and examination conditions before and after the same lesion (including scanning slice thickness, contrast agent, etc.). However, If patient has a contrast allergy or intolerance to contrast medium, a plain CT scan is allowed. During the treatment period, imageological examination and efficacy assessment should be repeated every 8 weeks (\pm 7 days) from C1D1 for the first 12 months, then every 12 weeks (\pm 7 days) thereafter until disease progression. Each imaging examination should be performed in accordance with the original imaging schedule, without adjustment due to dose delay. Tumor assessments will continue until disease progression and will not be interrupted due to discontinuation of the study treatment.

- CT/MRI examination in the screening period should be confirmed by the sponsor to be acceptable with the test results before the COD1 meeting the requirements (including the test results before the subject signs the informed consent form).
- Bone scan should be performed during the screening period. The bone scan during the screening period was performed by the sponsor to confirm the results of the research hospital within 42 days before the COD1 that could meet the research requirements (including the results of the examination before the subject signed the informed consent). Bone scan was performed only when there were clinical indications during the study period.
- The investigator may perform off-schedule imaging assessment at any time when disease progression is suspected. Subjects with a first CR or PR should be confirmed by imaging confirmation or the next efficacy evaluation after at least 4 weeks.

12. Using 18F-FES PET to monitor the detect in ER target occupation and inhibition

List of Abbreviations and Definitions of Terms

Abbreviation/ Specialist Term	Definition
AE	Adverse event
AUC _{0-t}	Area under the plasma concentration time curve
AUC _{0-inf}	The area under the plasma concentration-time curve from time 0 extrapolated to infinity.
AF1	Activation function 1
CL/F	Apparent clearance
C _{max}	Maximum concentration
CR	Complete response
C _{ave_ss}	Average concentration at steady status
C _{max_ss}	Maximum concentration at steady status
C _{min_ss}	Minimum concentration at steady status
CT	Computed tomography
CTCAE	Common terminology criteria for adverse events
DBD	DNA binding domain
DCR	Disease control rate
DF	Degree of fluctuation
DLT	Dose-limiting toxicity
DOR	Duration of response
ECG	Electrocardiogram
ECOG	Eastern Cooperative Oncology Group
ER+	Estrogen receptor positive
eCRF	Electronic case report form
GCP	Good Clinical Practice
GGT	Glutamyl transpeptidase
HED	Human equivalent dose
HIV	Human Immunodeficiency Virus
HNSTD	Highest non-severely toxic dose

Abbreviation/ Specialist Term	Definition
ICH	International Council for Harmonization of Technical Requirements for Pharmaceuticals for Human Use
LBD	Ligand binding domain
MAD	Maximum allowable dose
MRSD	Maximum recommended starting dose
MTD	Maximum tolerated dose
NMPA	National Medical Products Administration
ORR	Objective response rate
OS	Overall survival
PD	Progressive Disease
PFS	Progress free survival
PK	Pharmacokinetics
PKCS	Pharmacokinetics concentration set
PKPS	Pharmacokinetics parameter set
QD	Once-daily
RP2D	Recommended Phase II dose
SAE	Severe adverse event
SAP	Statistical analysis plan
SD	Stable disease
SERD	Selective estrogen receptor downregulator
SERM	Selective estrogen receptor modulators
SMC	Safety Monitoring Committee
SOC	System Organ Classification
SOP	Standard Operating Procedure
$t_{1/2}$	Elimination half life
TEAE	Treatment emergent adverse event
Tmax	Peak time
UBG	Urobilinogen
ULN	Upper Limits of Normal

Abbreviation/ Specialist Term	Definition
Vd/F	Apparent volume of distribution
V _{ss}	Steady state volume of distribution
λ_z	Elimination rate constant

1 Introduction

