
Investigational Product and Administration
	
FWD1802
 
 • Dosage Formulation: Tablet • Specification: 5 mg, 25 mg, 150 mg • Dosage Regimen: oral, once daily (QD). For details of dosage regimen for 8.2 Meals and Dietary Restrictions. • Storage: sealed containers, dry, $\leq 25^{\circ}\text{C}$, keep out of light.

Inclusion Criteria
	
 1. Patients must understand and voluntarily sign the Informed Consent Form (ICF). 2. Patients \geq 18 years, female. 3. Provision of blood sample to test ESR1 mutation status and for other biomarker assessment. In part A/B, the ESR1 mutation status will be tested retrospectively; In part C, only the patients with ESR1 mutation positive is eligible (See Appendix 6). 4. Documented positive oestrogen receptor status of primary or metastatic tumour tissue, according to the local laboratory

parameters. HER-2 negative. These laboratory parameters are consistent with accepted diagnostic guidelines such as the American Society of Clinical Oncology (ASCO) / College of American Pathologists (CAP) Clinical Practice Guideline for Pathologists estrogen (ER) and progesterone receptor (PgR) testing in breast cancer (Allison et al., 2020).

5. Menopausal women according to one of the following criteria:

- Prior bilateral ovariectomy;
- Patients \geq 60 years of age;
- Patients < 60 years of age presenting an amenorrhea of more than 12 months and follicle stimulating hormone (FSH) and plasma estradiol levels within the postmenopausal range as assessed by the local laboratory in the absence of chemotherapy, tamoxifen, tolimifene, or ovarian castration in the past 1 year, and no oral contraceptives, hormone replacement therapy, or gonadotropin-releasing hormone agonist or antagonist;
- Patients < 60 years of age who are taking either tamoxifen or tolimifene with two consecutive FSH and estradiol levels in the postmenopausal range.
- Or premenopausal or perimenopausal female subjects but must be willing to receive and maintain an approved luteinizing hormone-releasing hormone(LHRH) agonist during the study treatment period (LHRH agonist treatment initiated 28 days prior to the first study drug treatment); or for males: willing to receive and maintain an approved LHRH agonist during the study treatment period (LHRH agonist treatment initiated 28 days prior to the first study drug treatment).

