1.2.3 Toxicology

For safety evaluation, the MTDs from GLP-compliant single-dose oral toxicity studies were 400 or 200 mg/kg for male or female rats, respectively, and 200 mg/kg for dogs. Two 28-day repeated dose toxicity studies were conducted in rats and dogs. The STD10 in rats was considered to be 26 mg/kg/day and the HNSTD in dogs was 15 mg/kg/day.

FWD1802 when administered once daily for 28 days to rats was well tolerated. Test article-related adverse changes were limited to decreased food consumption and body weight gain in males at 26 mg/kg/day, and anatomic findings within ovaries and uterus in females at ≥ 6.5 mg/kg/day which were attributed to the intended pharmacology (selective estrogen receptor degrader) of the test article. Test article-related adverse changes in dogs were limited to histopathological findings in the reproductive tract in both sexes at ≥ 2.5 mg/kg/day.

In vitro genotoxicity studies showed there was no genotoxicity risk for FWD1802.

In summary, FWD1802 displayed a high degree of selectivity to ER, causing the ER to be degraded and thus downregulated. FWD1802 showed a significant growth inhibitory effect in ER-positive human breast cancer cell lines and MCF7 cell lines with ER α Y537S or

D538G mutation. FWD1802 monotherapy or combination with Palbociclib exhibit desired anti-tumor activity in the ER-positive or ESR1 Y537S mutation human breast cancer xenograft models. Besides, the potential toxicity of FWD1802 was well assessed in nonclinical safety assessments, and the results support the proposed phase 1 clinical trial with appropriate monitoring.

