5.2 Inclusion Criteria

1. Patients must understand and voluntarily sign the Informed Consent Form (ICF).
2. Patients \geq 18 years.
3. Provision of blood sample to test ESR1 mutation status and for other biomarker assessment. In part A/B, the ESR1 mutation status will be tested retrospectively; In part C, only the patients with ESR1 mutation positive is eligible (See Appendix 6).
4. Documented positive oestrogen receptor status of primary or metastatic tumour tissue, according to the local laboratory parameters. HER-2 negative. These laboratory parameters are consistent with accepted diagnostic guidelines such as the American Society of Clinical Oncology (ASCO) / College of American Pathologists (CAP) Clinical Practice Guideline for Pathologists estrogen (ER) and progesterone receptor (PgR) testing in breast cancer ([Allison et al., 2020](#)).
5. Menopausal women according to one of the following criteria:
 - Prior bilateral ovariectomy;
 - Patients \geq 60 years of age;
 - Patients $<$ 60 years of age presenting an amenorrhea of more than 12 months and follicle stimulating hormone (FSH) and plasma estradiol levels within the postmenopausal range as assessed by the local laboratory in the absence of chemotherapy, tamoxifen, tolimifene, or ovarian castration in the past 1 year, and no oral contraceptives, hormone replacement therapy, or gonadotropin-releasing hormone agonist or antagonist;
 - Patients $<$ 60 years of age who are taking either tamoxifen or tolimifene with two consecutive FSH and estradiol levels in the postmenopausal range.
 - Or premenopausal or perimenopausal female subjects but must be willing to receive and maintain an approved luteinizing hormone-releasing hormone(LHRH) agonist during the study treatment period (LHRH agonist treatment initiated 28 days prior to the first study drug treatment); or for males: willing to receive and

maintain an approved LHRH agonist during the study treatment period (LHRH agonist treatment initiated 28 days prior to the first study drug treatment).

6. Previous therapy failed or intolerable, or standard therapy not available:

Part A/C: Previous therapy failed or intolerable, or standard therapy not available.

Part B/C: Patients should have received at least 1 line ET, or received no more than 1-line systematic chemotherapy for advanced/metastatic disease, no more than 1 target therapy.

7. Patients who are HIV positive with CD4+ T-cell counts ≥ 350 cells/uL may be eligible.

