8. Eastern Cooperative Oncology Group (ECOG) performance status of 0 or 1.
9. At least one measurable lesion according to RECISTv1.1 criteria.
10. Life expectancy ≥ 12 weeks.
11. Adequate organ and bone marrow function (no use of hematopoietic stimulating factor, no blood transfusion or human albumin within 7 days prior to screening):
- Blood routine: Absolute neutrophil count (ANC) $\geq 1.5 \times 10^9/L$; Platelet count (PLT) $\geq 100 \times 10^9/L$; Hemoglobin (HGB) ≥ 90 g/L;
 - Liver function: Serum Total bilirubin (TBIL) ≤ 1.5 Upper limit of normal value (ULN); Alanine aminotransferase (ALT) and Aspartate transferase (AST) $\leq 3 \times ULN$ in subjects without liver metastasis; ALT or AST $\leq 5 \times ULN$ with liver metastasis;
 - Renal function: Serum creatinine $\leq 1.5 \times ULN$ or estimated creatinine clearance (CLcr) ≥ 60 mL/min as calculated using Cockcroft-Gault formula;
 - Coagulation function: Activated Partial thromboplastin Time (APTT) and international normalized ratio (INR) $\leq 1.5 \times ULN$ (or within target range if on anticoagulation therapy);
 - Cardiac function: Echocardiography (ECHO) shows left ventricular ejection fraction (LVEF) $> 50\%$.
12. Women of childbearing potential must have a negative serum pregnancy test within 7 days prior to the first dose. Female patients of childbearing potential must agree to use effective methods of contraception from the time of signature of informed consent, throughout the study and for 6 months after the last dose of the investigational product, like double barrier methods, condoms, oral or injectable contraceptives, intrauterine devices, etc. All female subjects will be considered to be of childbearing potential

unless they are postmenopausal, postmenopausal, or sterilized (hysterectomy, tubal resection).

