9.5.4 Pregnancy

The risks of treatment with FWD1802 during pregnancy have not been evaluated. To ensure participant's safety, each pregnancy in a subject on drug must be reported to the sponsor within 24 h of learning of its occurrence. The pregnancy should be followed up to determine outcome, including spontaneous or voluntary termination, details of the birth, and presence or absence of any birth defects, congenital abnormalities, or maternal and/or newborn complications. Pregnancy and follow-up will be documented, and should include

an assessment of the possible relationship to the IND drug of any pregnancy outcome. Pregnant women who are abortive or need induction of labor should be reported as an SAE.

Pregnancy outcomes must also be collected for the female partners of any males who takes study treatment in the trial, pending consent from the mother.

10 Statistics

A Statistical Analysis Plan (SAP) will be written prior to database lock. The SAP will detail the planned statistical analysis methods to be conducted. A summary of the proposed statistical analysis plan to be conducted is provided in the following sections.

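### The synopsis limits entry to females yet sets a condition for males, Section 5.2 has no sex limit, and no contraception duty is addressed to male subjects

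*Protocol*

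**What the plan says.** **Who may enter.** Synopsis inclusion criterion 2 asks for patients of at least "18 years, female". The last bullet of synopsis criterion 5 then provides for men: "or for males: willing to receive and maintain an approved LHRH agonist during the study treatment period". In Section 5.2, criterion 2 keeps the age limit and omits sex. Criterion 5 there opens with "Menopausal women according to one of the following criteria", but its last bullet again turns to men: "or for males: willing to receive and" maintain an LHRH agonist.

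**Other text that expects men.** Note 7 to each of Tables 1, 2 and 3 gives a separate QTcF value for males as a trigger for further ECGs. Section 8.1.1 defines when a male subject counts as fertile. Section 9.5.4 states: "Pregnancy outcomes must also be collected for the female partners of any males who takes study treatment".

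**Contraception.** Section 5.2 criterion 12, with the same text in synopsis criterion 11, says: "Female patients of childbearing potential must agree to use effective methods of contraception". Section 8.1.2 is limited to female subjects in both its title and its requirements. Section 9.5.4 adds that the risks of FWD1802 in pregnancy have not been evaluated.

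**The concern.** Eligibility is an operative rule, and two current parts of the same protocol version answer it differently for a man. A site that applies synopsis criterion 2 would turn him away. A site that applies Section 5.2 would admit him if he met the LHRH condition. Nothing says which text prevails, so the same enrolment could be recorded as valid at one site and as an eligibility deviation at another.

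The second matter depends on the first. If men may enter, the protocol defines their fertility and follows pregnancies in their partners, but places no contraception duty on them and sets no duration for one. Eligibility and contraception are protocol matters, so a statistical analysis plan could not settle either.

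**Working it through.** No arithmetic applies. The check sets the relevant passages side by side.

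**1. Are men eligible?**

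| Place | What it implies for men |
|---|---|
| Synopsis, criterion 2 | Not eligible |
| Synopsis, criterion 5, last bullet | Eligible on an LHRH condition |
| Section 5.2, criterion 2 | No sex limit |
| Section 5.2, criterion 5, opening line | Names women only |
| Section 5.2, criterion 5, last bullet | Eligible on an LHRH condition |
| Tables 1 to 3, note 7 | Men expected (male QTcF trigger) |
| Section 8.1.1 | Men expected (fertile male subject defined) |
| Section 9.5.4 | Men expected (partners of treated men) |

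The first two rows cannot both hold. The first row also conflicts with both Section 5.2 criteria, so the contradiction lies inside the synopsis as well as between synopsis and body. The opening line of criterion 5 is a lesser mismatch: the male clause is filed as one way of being a menopausal woman.

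Three further passages point the same way. Exclusion 5 makes an exception for a prostatic lesion, Section 7.4.1 uses pronouns of both sexes for the person being screened, and Section 10.4 lists gender among the baseline summaries. None of them states a rule on eligibility.

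**2. Is any contraception duty placed on a male subject?**

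| Place | Addressed to |
|---|---|
| Synopsis, criterion 11 | Females |
| Section 5.2, criterion 12 | Females |
| Section 8.1.1 | Both sexes, but a definition only |
| Section 8.1.2 | Females |
| Section 8.1.3 | A list of methods; vasectomy appears for a male partner |
| Sections 8.1.3.1 and 8.1.4 | Lists of methods; no duty on a male subject |
| Section 9.5.4 | Partners of treated men, but reporting only |

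Three places impose a duty, and all three address females. The table of contents lists no male counterpart to Section 8.1.2. The male definition in Section 8.1.1 therefore leads to no requirement, and Section 9.5.4 acts only once a pregnancy has occurred.

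**3. Background.** Section 1.2.3 reports adverse changes in dogs described as "histopathological findings in the reproductive tract in both sexes". This shows that the nonclinical findings were not confined to females. The point does not rest on it.

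**The case against.** The best defence is that the intent can be read from the body. Section 5.2 has no sex limit and a male clause, and several later sections expect men. On that reading the synopsis carries one stray word. This stands in part: the weight of the text favours admitting men, and the practical ambiguity is narrower than a flat contradiction suggests. But the stray word sits in an eligibility criterion and nothing gives the body precedence. If men are admitted, the contraception mismatch becomes live.

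It can also be said that Section 9.5.4 partly covers the matter by collecting partner pregnancy outcomes. It does, as follow-up; it is not a preventive requirement. Nor does the protocol say that the LHRH condition stands in for contraception, and Section 8.1.1 treats a man as fertile unless he is permanently sterile.

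Three stronger readings are tempting, and the document does not support them:

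- **A conflict of QTcF limits.** A reader might set the 470 ms limit in exclusion 12 against the 450 ms male value in the ECG notes. The first is an entry exclusion; the second only triggers three consecutive ECGs to obtain a mean. They are different rules. The ECG notes show only that men are expected.
- **Lost DLT evidence.** A reader might infer that a man of disputed eligibility would drop out of a three-patient cohort. Section 4.4 counts enrolled subjects. The full analysis set (10.2.1) needs one dose, and the safety set (10.2.2) needs dosing and one valid safety assessment. None of these removes a dosed patient for ineligibility.
- **Demonstrated harm through the male.** A reader might take the dog findings as evidence of risk to a partner or offspring. Section 1.2.3 reports tissue findings in the treated animals and says that in vitro studies showed no genotoxicity risk. The firmer ground is Section 9.5.4, which says that risk in pregnancy is unevaluated.

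**Conclusion.** The point holds as an internal inconsistency with two parts. First, synopsis criterion 2 conflicts with synopsis criterion 5 and with Section 5.2 criteria 2 and 5 on whether men may enter. Second, the protocol expects fertile treated men in Sections 8.1.1 and 9.5.4, while all three statements of a contraception duty address females only.

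The size is limited. The planned 99 subjects, the cohort sizes, the endpoints and the analyses are untouched. The protocol gives no expected number of men, so no count of affected participants is offered. For any man who presents, though, the text gives no single answer on entry and no contraception rule if he is treated. The conclusion rests only on the wording of the current protocol and takes no position on which eligibility or contraception rule is right. It should be corrected.

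**What to change.** Reconcile synopsis criteria 2 and 5 with Section 5.2 criteria 2 and 5, so that both lists give the same answer on sex and the opening line of criterion 5 fits the bullets beneath it. Then follow one of two routes:

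- If men are eligible, reconcile Section 8.1.2, and the matching eligibility criteria (synopsis 11, Section 5.2 criterion 12), with Sections 8.1.1 and 9.5.4 so that male subjects are addressed. The content of that provision is for the sponsor and investigators to decide.
- If men are not eligible, add the restriction to Section 5.2 and remove the male clauses from criterion 5 in both lists, Section 8.1.1, Section 9.5.4 and note 7 of Tables 1 to 3.

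The cost is protocol wording, with the ethics review that Section 12.2 requires for protocol changes. No design parameter or analysis needs to be redone.

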Statistical Methods	
Descriptive analysis (summary statistics) will be used to describe the safety and efficacy endpoints.
 
Safety Analysis:
 
Incidence and severity of adverse events according to the NCI-CTCAE (V5.0) will be summarized and displayed in number/percentage. The exposure extent to the study drug will be displayed.. 
Efficacy Analysis:
 
The ORR and its exact 95% Clopper-Pearson confidence interval will be calculated. The CBR, DCR will also be calculated similarly. All of the time-to-event data (PFS, DOR, OS) will be estimated using Kaplan-Meier method, and the median along with two-sided 95% CI will be displayed (use the Greenwood's formula for estimation of standard errors). 
Pharmacokinetic analysis:
 
A descriptive analysis of the plasma concentration and derived PK parameters of FWD1802 and its metabolite (if possible) will be conducted by dose level. Plasma concentration patient profiles versus time and mean concentration versus time will be displayed.

Table 1 Schedule of Events in Part A Dose Escalation

Items	Screening ¹	Single dose			Multiple dose							Follow-up		
		4 days			Cycle 1 28days				Cycle 2		≥Cycle3	EOT ₂	SFU ₃	LTFU ⁴
Visit Day	D-28~ D-1	D 1	D2~ D4		D1	D8	D1 5	D2 2	D1	D15	D 1			
Evaluation Window (Days)	0	0	0	0	0	± 1	± 1	± 1	± 3	± 3	± 3	± 7	± 7	± 7
Administrative Procedures														
Informed Consent	X													
Inclusion/Exclusion Criteria	X													
Demographics	X													
Medical history	X													
Concurrent diseases	X													
Clinical Procedures/Assessments														
Weight	X	X			X	X	X	X	X	X	X	X		
Body height	X	X			X	X	X	X	X	X	X	X		
Physical examination ⁵	X	X	X		X	X	X	X	X	X	X	X		
Vital signs ⁶	X	X	X		X	X	X	X	X	X	X	X		
ECOG Score	X	X	X		X	X	X	X	X	X	X	X		
12-lead ECG ⁷	X	X			X	X	X	X	X	X	X	X		
Echocardiogram	X				X						X (Every 3weeks)			
Laboratory Assessments														
Blood Chemistry	X	X*			X	X	X	X	X	X	X	X		
Hematology	X	X*			X	X	X	X	X	X	X	X		
Coagulation	X	X*			X	X	X	X	X	X	X	X		
Urinalysis	X	X*			X	X	X	X	X	X	X	X		
Virology: HBV, HCV, and HIV ⁸	X													
Pregnancy ⁹	X													
COVID-19 ¹⁰	X													

Items	Screening ¹	Single dose			Multiple dose							Follow-up		
		4 days			Cycle 1 28days				Cycle 2		≥Cycle3	EOT ₂	SFU ₃	LTFU ⁴
Visit Day	D-28~ D-1	D 1	D2~ D4		D1	D8	D1 5	D2 2	D1	D15	D 1			

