6. Vital signs include temperature, pulse, breathing and blood pressure. On C0D1 and C1D1, the vital signs will be measured at pre-morning dose(s), and 0.5 h, 2 h, 4 h, 8 h, 12 h and 24 h after the morning dose(s). On C0D3, C0D4, C1D8, C1D15, C1D22, C2D1, C2D15, (C3~Cn) D1, the vital signs will be measured at pre-morning dose(s). Other examinations may be conducted if deemed clinically necessary by the investigator.
7. 12-lead ECG will be performed three times at Screening, 30 min, 20 min and 10 min pre-dose and 0.5 h, 1 h, 1.5 h, 2 h, 3 h, 4 h, 5 h, 6 h, 8 h, 12 h and 24 h post-dose on C0D1 and C1D1, and the spacing between each ECG examination will be at least 1 min. On C1D8, C1D15, C1D22, C2D1, C2D15, (C3~Cn) D1, the 12-lead ECG will be measured at pre-morning dose(s) and 2 h after the morning dose(s). Meanwhile, 12-lead ECG will be performed on prematurely withdrawn. If QTcF > 450 ms (male) or > 470 ms (female), 3 consecutive ECGs should be collected to calculate the mean QTcF value.
8. Human immunodeficiency virus antibody, hepatitis B surface antigen, hepatitis B core antibody, hepatitis C virus antibody, and Treponema pallidum antibody. period and may optionally be done at additional time points depending on investigator discretion.
9. Only applicable to women of childbearing age; Subjects must have a negative blood pregnancy test during the screening period. Pregnancy tests will be performed anytime during the course of the study, as per investigator's discretion. Serum or urine tests are acceptable based on the site's standard clinical practice, if a urine pregnancy test is positive, it must be confirmed by a serum pregnancy test.
10. Infectious disease screening includes polymerase chain reaction for SARS-CoV-2;
11. Blood will be collected for PK analysis of the FWD1802 Tablet and/or its metabolites (if any), details please refer to 7.5.1 PK Samples.
12. Tumor assessment: All patients will undergo MRI, chest, abdomen, pelvis and bone examination at baseline period, and subsequent imageological examination included the chest, abdomen, pelvis, and other metastatic sites, if any. The preferred

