1.4.2 Risk control in trial design

In the clinical study, a series of examinations (exams) at the screening and treatment period will be conducted. The frequency of the clinical laboratory (lab) tests such as blood biochemistry will be increased accordingly, if needed. Additional tests may be added, if deemed necessary. Additional risk to subjects include those attributable to study participation in general, including risks associated with frequent medical tests and laboratory blood draws, and the associated pain and discomfort.

Strategies to mitigate these risks include close monitoring of adverse events (AEs) and lab results. Both individual and trial stopping criteria will be specified, AEs will be assessed in this protocol, and AEs of special interest will be paid extra attention. Supportive care and risk control management will also be provided to subjects, including appropriate treatment of any AEs. The risk to participants in this trial will be minimized by adherence to the eligibility criteria, closely clinical monitoring and stopping rules.

Overall, the nonclinical data showed a positive benefit/risk ratio to support the clinical development of FWD1802 with appropriate safety monitoring. Data obtained from this

study will be provided to support later stages of clinical development for FWD1802 to be conducted in selected populations.

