11. Subjects with known active hepatitis B virus (HBV) or hepatitis C virus (HCV) infection with abnormal liver function (Absence of infection was defined as HBsAg negative, HBV DNA negative and HCV antibody negative), except to:
 - Subjects who test positive for HBsAg or HBsAb during the screening period may be enrolled if the PCR test result for HCV-RNA is < 500 IU/ml (2000 copies/mL), but receive antiviral treatment according to the investigator's assessment and undergo PCR for HBV-DNA during the study treatment period;
 - Subject has a positive test for HCV antibody at screening and can be enrolled if the PCR test result for HCV-RNA is negative.
12. History of clinically significant cardiovascular disease, such as:
 - Symptomatic congestive heart failure according to New York Heart Association Grades (NYHA $>$ Grade 2);
 - Severe/unstable angina, new angina within last 3 months;
 - Myocardial ischemia and long-term use of drugs for control; according to NYHA, grade III-IV cardiac insufficiency;
 - Any event of acute myocardial infarction within 6 months before screening;
 - Any grade ≥ 2 supraventricular arrhythmia or ventricular arrhythmia requiring treatment or intervention;
 - Any grade atrial fibrillation, coronary/peripheral artery bypass graft, or cerebrovascular symptoms including transient ischemic attack;
 - QTcF (Fridericia's correction formula used) > 470 ms;
 - ECG < 50 bpm.
13. History of serious allergic reactions to the study drugs or excipients used in the protocol.
14. Women who are pregnant or lactating.
15. Prior use of an oral selective estrogen receptor degrader (SERD).
16. Subjects who use drugs or herbal supplements known to be moderate/strong inhibitors of CYP3A2 weeks prior to the first study drug treatment. Subjects who use drugs or herbal supplements known to be moderate/strong inducers of CYP3A4 weeks prior to the first study drug treatment.
17. Received medications which inhibits the production of stomach acid within 2 weeks or 5 drug half-lives (whichever is longer) prior to the first dose of study drugs.

18. Received medications which inhibits P-gp within 2 weeks or 5 drug half-lives (whichever is longer) prior to the first dose of study drugs.
19. Patients with active or chronic corneal disease, other active eye disease requiring ongoing treatment, or any clinically significant corneal disease for which drug-induced keratopathy cannot be adequately monitored.

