7.3 Description of Assessments

7.3.1 Laboratory Assessments

All protocol required clinical laboratory assessments should be performed at the investigational site's local laboratory. All clinical laboratory results must be documented on the CRF and reference ranges and safety parameters must be provided for each laboratory used. The following assessments will be performed and evaluated during the study.

Table 10 Laboratory Assessments

Hematology	red blood cell counts (RBC), white blood cell counts (WBC), and differential counts (neutrophils (NE), lymphocytes (LY#), monocytes (MO#), eosinophils (EO#), and basophils (BA)), platelet count (PLT), hemoglobin (HGB), and hematocrit (HCT)
Coagulation Function	PT (Prothrombin Time), APTT (Partial Thromboplastin Time), INR (International Normalized Ratio), Thrombin time (TT) and fibrinogen (FIB)
Fasting Serum Biochemistry	ALT, AST (Aspartate Transaminase), GGT (Gamma-glutamyl Transpeptidase), TBIL (total bilirubin), DBIL (direct bilirubin), BUN (Urea Nitrogen) or urea, Cr (Creatinine), UA (uric acid), GLU (blood glucose), potassium, sodium, chlorine, calcium, phosphate, magnesium, TP (total protein), ALB (albumin), albumin/globulin ratio, LDH (Lactate Dehydrogenase), TBA (Total Bile Acid), TG (Triglyceride), CK (Creatine kinase), CK-MB (creatinine kinase isoenzyme) and ALP (Alkaline Phosphatase).

Pregnancy Test	serum β -Human Chorionic Gonadotropin (β -HCG). Lack of childbearing potential must be noted in the source documents, if applicable.
Urinalysis	specific gravity, pH, white blood cells, red blood cells, α 1 microglobulin, β macroglobulin, occult blood, proteins and glucose.
Infectious Disease Screening	HCV, HBV, HIV, syphilis, etc., but if the subject can present the test results done within 4 weeks prior to the administration, the screening can be exempted.

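### Exclusion 11's hepatitis B exception limits HCV RNA instead of HBV DNA, names an antibody the screening panel does not test, and requires an on-treatment PCR that no schedule lists

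*Protocol*

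**What the plan says.** Exclusion 11 applies to patients with "known active hepatitis B virus (HBV) or hepatitis C virus (HCV) infection with abnormal liver function". It defines absence of infection as negative HBsAg, negative HBV DNA and negative HCV antibody, and then gives two exceptions.

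- **Hepatitis B:** "Subjects who test positive for HBsAg or HBsAb during the screening period may be enrolled", and the condition is "if the PCR test result for HCV-RNA is < 500 IU/ml (2000 copies/mL"). They are to receive antiviral treatment as the investigator judges and to "undergo PCR for HBV-DNA during the study treatment period".
- **Hepatitis C:** patients with HCV antibody may enrol if HCV RNA is negative.

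The synopsis carries the same wording.

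In Tables 1, 2 and 3 the row "Virology: HBV, HCV, and HIV" has a mark under screening and nowhere else. Note 8 to each table itemises the panel as HIV antibody plus "hepatitis B surface antigen, hepatitis B core antibody, hepatitis C virus antibody, and Treponema pallidum antibody". Section 7.4.1 lists virology at screening. Section 7.4.2 only refers back to the tables. The end-of-treatment list and the safety follow-up text in 7.4.3 contain no virology.

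**The concern.** An exception of this kind has three jobs: to name the marker that brings a patient under it, to set the viral load at which she may enter, and to say how she is watched on treatment. Here each job has a fault. The viral-load limit is set on the wrong virus. One of the two markers is not in the panel. The monitoring is required but appears in no schedule.

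What is at stake is the safety of a few patients with hepatitis B in a first-in-human study. Read literally, the exception admits a patient whatever her HBV DNA. A site that works from the visit tables, as sites do, would not order the PCR that criterion 11 demands after enrolment.

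**Working it through.** There is no planned figure to reproduce. The check sets criterion 11 beside the schedule.

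**Viral-load limit**

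| Exception | Patients | Limit stated |
|---|---|---|
| Hepatitis B | HBsAg or HBsAb positive | HCV RNA below 500 IU/ml |
| Hepatitis C | HCV antibody positive | HCV RNA negative |

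Both limits are on HCV RNA. The first says nothing about HBV DNA. It also disagrees with the second for a patient positive for both viruses: detectable HCV RNA below 500 IU/ml passes the first and fails the second. The requirement later in the same sentence is for HBV DNA. The simplest explanation is that HCV-RNA is a misprint for HBV-DNA.

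**Markers**

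| Marker | Exception in criterion 11 | Panel in note 8 |
|---|---|---|
| HBsAg | yes | yes |
| Surface antibody (HBsAb) | yes | no |
| Core antibody (HBcAb) | no | yes |
| HBV DNA | on treatment; also in the definition of absence of infection | no |

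Only HBsAg is in both the trigger and the panel. Note 8 has the same panel under all three tables, whereas HBsAb occurs only in criterion 11, a sentence that already contains one likely misprint. The more economical reading is that HBsAb should be HBcAb and that the panel is right.

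**On-treatment HBV-DNA time points**

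| Place | Time points |
|---|---|
| Table 1 | 0 |
| Table 2 | 0 |
| Table 3 | 0 |
| Table 10 | 0 |
| Section 7.4 | 0 |

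HBV DNA is named nowhere in the protocol except in criterion 11.

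**Can existing draws carry the test?** Blood chemistry is marked on Day 1 of Cycle 1, Cycle 2 and every later cycle in all three tables. Cycles last 28 days, and the window is ±3 days from Cycle 2 Day 1 on. Two consecutive Day 1 visits from Cycle 2 on are then 28 − 6 = 22 to 28 + 6 = 34 days apart. This shows only that no new visit is needed. It does not say what the interval should be.

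**The case against.** The strongest reply is that the obligation is already there. Criterion 11 makes the PCR mandatory, a site that omits it breaches the criterion, and the tables do not authorise the omission. The requirement follows a reference to the investigator's assessment, so timing may have been left to the investigator. Section 1.4.2 adds "Additional tests may be added, if deemed necessary", liver enzymes and bilirubin are measured at every chemistry visit, and these patients receive antiviral treatment as the investigator judges. All of this reduces the risk. None of it schedules the test, and liver chemistry does not measure HBV DNA. Nor does it touch the wrong analyte or the antibody mismatch.

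The lead clause is also narrow: it covers known active infection with abnormal liver function. That limits how many patients need the exception. It does not empty it, because the inclusion criteria accept ALT and AST up to 3×ULN, or 5×ULN with liver metastasis.

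A reader might infer more than the text supports in three places:

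- **A patient positive only for core antibody is left without instruction.** Under the lead clause and the definition of absence of infection, neither antibody excludes anyone by itself, so the mismatch blocks no enrolment.
- **Table 10 opens a gap** because "if the subject can present the test results done within 4 weeks prior to the administration, the screening can be exempted". The natural reading is that outside results stand in for the same tests, within a period equal to the 28-day screening window. No wrong statement is shown.
- **Note 8 makes later virology optional.** Its second sentence starts mid-phrase in all three tables, so nothing can be built on it in either direction.

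**Conclusion.** The point holds as a minor safety and eligibility correction. Criterion 11's hepatitis B exception is wrong as written in both places where it stands: it sets no limit on HBV DNA, and it names a marker that the panel does not include. The on-treatment PCR it requires has no time point in any table or section.

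The missing time point is plain from the text. That HCV-RNA and HBsAb are misprints is an inference, a strong one for the analyte and a reasonable one for the antibody. If the sponsor did mean surface antibody, the panel would need it added instead. The missing PCR row remains on either reading.

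The size cannot be given in patients. The protocol does not say how many would enter under the exception, and none is assumed here. It would be wrong to infer that patients with uncontrolled hepatitis B will enter in any number, or that the trial's results are affected. No endpoint, analysis or sample size depends on this rule.

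**What to change.** 1. In criterion 11, in both the synopsis and 5.3, change HCV-RNA to HBV-DNA in the hepatitis B exception and HBsAb to HBcAb. HBV DNA then becomes a screening test for patients positive on these markers who need the exception, with no separate rule. Leave the HCV RNA condition in the hepatitis C exception as it is.
2. Add to each of Tables 1-3 a conditional HBV-DNA row for patients enrolled under the exception, drawn with the existing Day 1 chemistry sample. The sponsor's clinicians should set the interval and confirm the antibody.

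The cost is two word changes in each of two places (four in all), one row in each of three tables, and a few PCR tests in a small subset. The on-treatment tests are already required. No visit is added, and note 8 and Table 10 can stay as they are.
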